CYP	Cytochrome P450
DCR	Disease control rate
DLT	Dose-limiting toxicity
DOOR	Duration of response
ECG	Electrocardiogram
ECOG	Eastern Cooperative Oncology Group
eCRF	Electronic case report form
EOT	End of treatment/end of therapy
FGFR	Fibroblast growth factor receptor
GCP	Good Clinical Practice
iCCA	Intrahepatic cholangiocarcinoma
ICF	Informed consent form
ICH	International Council for Harmonisation of Technical Requirements
IEC	Independent Ethics Committee

Abbreviation	Definition
IND	Investigational New Drug
ir	Immune-related
IRB	Institutional Review Board
I.V.	Intravenous
MRI	Magnetic resonance imaging
NCI	National Cancer Institute
CCI	CCI [REDACTED]
ORR	Objective response rate
OS	Overall survival
PD	Progressive disease
PD-1	Programmed death-ligand 1
PD-L1	Programmed cell death ligand 1
PD-L2	Programmed cell death ligand 2
PFS	Progression free survival
P-gp	P-glycoprotein
CCI	CCI [REDACTED]
PO	Oral
PR	Partial response
PT	Preferred term
QD	Once daily
QTcF	QT interval corrected for heart rate using Fridericia's formula
RECIST 1.1	Response Evaluation Criteria in Solid Tumors, Version 1.1
SAE	Serious adverse event
SAP	Statistical analysis plan
SD	Stable disease
SOP	Standard operating procedure
TEAE	Treatment-emergent adverse event
TOI	Taiho Oncology, Inc.

Abbreviation	Definition
UC	Urothelial carcinoma / cancer
ULN	Upper limit of normal
WOCBP	Women of childbearing potential
WT	Wild-type

1. INTRODUCTION

1.1. Urothelial Carcinoma

Cancers affecting the surface epithelium of the renal collecting tubules, calyces, pelvis, ureter, bladder, and urethra (collectively “urothelium”) are broadly divided into two categories: upper tract urothelial carcinoma (UTUC), which accounts for approximately 5-10% of cases; and urinary bladder cancer (UBC), which accounts for the remainder ([Miyazaki and Nishiyama 2017](#)). UBC is more common in men than in women, with age-standardized incidence rates for more developed regions of around 16.3 per 100,000 for the former and 3.6 per 100,000 for the latter ([Ferlay et al. 2010](#)).

For patients with advanced disease, systemic platinum-based chemotherapy is the standard treatment, and may improve overall survival (OS) from 6 months or less with untreated disease to 12-15 months ([von der Maase et al. 2000](#); [van der Maase et al. 2005](#)). However, long-term prognosis is poor; the 5-year survival of patients with advanced disease is approximately 15% ([von der Maase et al. 2005](#)). Moreover, platinum-based chemotherapy is associated with substantial toxicity, which may render it unsuitable for some patients. New therapeutic options are needed for patients with advanced urothelial carcinomas (UC) who progress on or are not candidates for standard therapy.

1.2. Pembrolizumab

The importance of intact immune surveillance function in controlling outgrowth of neoplastic transformations has been known for decades ([Disis 2010](#)). Accumulating evidence shows a correlation between tumor-infiltrating lymphocytes in cancer tissue and favorable prognosis in various malignancies. In particular, the presence of CD8+ T-cells and the ratio of CD8+ effector T-cells/FoxP3+ regulatory T cells (T-reg) correlates with improved prognosis and long-term survival in solid malignancies, such as ovarian, colorectal, and pancreatic cancer; hepatocellular carcinoma; malignant melanoma; and renal cell carcinoma.

The programmed death-ligand 1 (PD-1) receptor-ligand interaction is a major pathway that is hijacked by tumors to suppress immune control. The normal function of PD-1, expressed on the cell surface of activated T-cells under healthy conditions, is to down-modulate unwanted or excessive immune responses, including autoimmune reactions.

Pembrolizumab is a potent humanized immunoglobulin G4 (IgG4) monoclonal antibody (mAb) with high specificity of binding to the programmed cell death 1 (PD-1) receptor, thus inhibiting its interaction with programmed cell death ligand 1 (PD-L1) and programmed cell death ligand 2 (PD-L2). Based on preclinical in vitro data, pembrolizumab has high affinity and potent receptor blocking activity for PD-1. Pembrolizumab is indicated for the treatment of patients across a number of indications, and is associated with an acceptable preclinical and clinical safety profile as an intravenous (I.V.) immunotherapy for advanced malignancies.

Prior studies have demonstrated that fibroblast growth factor receptor 3 (*FGFR3*)-mutant UCs are associated with decreased T-cell infiltration. As *FGFR3* mutations are enriched in luminal-like UC, and luminal-like UC has been shown to be relatively less responsive to PD-1/PD-L1 inhibition (checkpoint inhibition [CPI]), these data have led to the speculation that *FGFR3*

mutations may be causally related to poor T-cell infiltration and that UC patients harboring *FGFR3* mutations may be suboptimal candidates for CPI such as pembrolizumab.

However, [Wang et al. \(2018\)](#) determined that while *FGFR3*-mutant UC is associated with a similar tumor mutational burden and lower T-cell infiltration, it is also associated with lower stromal/transforming growth factor beta (TGF- β) immune suppressive signals. These findings suggest that *FGFR3* mutation status may not in fact be a biomarker of resistance to CPI, and provides a rationale for the combination of FGFR-targeted treatment with CPI treatment.

Moreover, recently published data ([Palakurthi et al. 2019](#)) shows that FGFR inhibition and anti-PD-1 combination induced significant tumor regression and improved survival. For both erdafitinib monotherapy and combination treatments, tumor control was accompanied by tumor-intrinsic, FGFR pathway inhibition, increased T-cell infiltration, decreased regulatory T cells, and downregulation of PD-L1 expression on tumor cells. Finally, FGFR inhibition may also modulate the tumor microenvironment in non-*FGFR3*-mutated tumors through the blockade of paracrine fibroblast growth factors (FGF) signaling, targeting immune evasion and angiogenesis and lead to enhanced efficacy when combined with pembrolizumab in both wild-type (WT) and *FGFR3* mutated tumors ([Ichikawa et al. 2020](#); [Liu et al. 2014](#); [Siefker-Radtke et al. 2018](#)).

1.3. Futibatinib (TAS-120)

1.3.1. Background

The fibroblast growth factor/fibroblast growth factor receptor (FGF/FGFR) signaling axis has been well characterized for its role in proliferation, differentiation, migration, and survival of cells, and it is fundamental to embryonic development, regulation of angiogenesis, and wound healing in adults. Accordingly, dysregulation of this signaling pathway has been associated with many developmental disorders and cancer.

Futibatinib is a novel and selective small molecule FGFR inhibitor, which is the first irreversible, covalent inhibitor of FGFR1–4 being tested in humans. Futibatinib selectively and irreversibly binds to FGFR to exert an inhibitory effect on the FGF/FGFR pathway. Preclinical studies have shown that futibatinib selectively inhibits the cell growth of human cancer cell lines bearing FGFR gene abnormalities; strong antitumor efficacy has been observed with futibatinib in nude mouse or nude rat xenograft models bearing tumors with FGFR gene abnormalities.

1.3.2. Clinical Overview

As of 05 September 2019, a total of 460 subjects (41 healthy volunteers and 419 patients) have been treated with futibatinib across 4 clinical trials. To date, 2 clinical studies in healthy volunteers have been completed, and 2 Phase 1-2 studies assessing the safety, efficacy, and pharmacokinetics (PK) of futibatinib in advanced cancers are currently ongoing.

The recommended dose and schedule of futibatinib is 20 mg QD (continuous daily dosing), based on the results of a Phase 1 dose escalation study (TAS-120-101). Accordingly, the starting dose of futibatinib in this Phase 2 study is 20 mg QD.

In all, more than 460 patients and healthy volunteers have been treated with futibatinib across all trials. Collectively, safety data from these studies suggest that futibatinib is associated with manageable toxicity in multiple patient populations. The most frequently reported treatment-

related adverse event (AE) overall has been hyperphosphatemia (a mechanism-based event), mostly of Grades 1-2 and without clinical complications. Other frequently reported treatment-related AEs included the gastrointestinal system disorders of diarrhoea, dry mouth, nausea, and stomatitis. Skin toxicity and increased liver enzymes have also been reported, most of which have been mild to moderate in severity. Ocular toxicities, which have been reported with other FGFR inhibitors, were observed with low frequency in all trials.

Efficacy has been observed in different tumor types:

- Solid tumors harboring *FGFR1-4* rearrangements, including intrahepatic cholangiocarcinoma (iCCA), head and neck, unknown primary, and gastric cancer
- Gastric cancer with *FGFR2* amplification
- Myeloid/lymphoid neoplasm with *FGFR1* rearrangement
- Other solid tumors with different *FGFR* aberrations

Refer to the Investigator's Brochure for more detailed background information on futibatinib.

1.4. Summary of Study Rationale

Advanced UC is associated with very poor long term prognosis; even with standard therapy, the majority of patients will progress and the 5-year survival rate remains only approximately 15%. Moreover, many patients are unable to tolerate standard chemotherapy; for such patients, therapeutic options are even more limited. There is evidence that the combination of a PD-1/PD-L1 inhibitor and an FGFR inhibitor may result in treatment benefit in this population. This Phase 2 study will assess the effect of pembrolizumab and futibatinib on patients with UC, including patients with *FGFR3* mutation / *FGFR1-4* fusion/rearrangement.

2. OBJECTIVES AND ENDPOINTS

The objectives and endpoints of this study are shown in [Table 3](#).

All variables based on tumor response will be calculated based on the Response Evaluation Criteria in Solid Tumors, Version 1.1 (RECIST 1.1), as well as iRECIST criteria. The primary evaluation of efficacy will be based on RECIST 1.1. All evaluations of tumor response will be per local Investigator/radiologist assessment.

Table 3: Objectives and Endpoints

[figure not shown]
Primary	
Objective response rate (ORR)	
ORR, defined as the proportion of patients experiencing a best overall response of partial response (PR) or complete response (CR).
Secondary	

Disease control rate (DCR)Duration of response (DOR)Progression-free survival (PFS)Overall survival (OS)Safety and tolerability	
DCR, defined as the proportion of patients experiencing a best overall response of stable disease (SD), PR, or CR.DOR defined as the time from the first documentation of response (CR or PR) to the first documentation of objective tumor progression or death due to any cause, whichever occurs first.PFS, defined as the time from first dose of study therapy to the date of death (any cause) or disease progression, whichever occurs first.OS, defined as the time from the date of first dose to the death date.Safety based on reported AEs and on-study laboratory parameters, graded according to the National Cancer Institute—Common Terminology Criteria for Adverse Events (NCI-CTCAE), Version 5.0.
Exploratory Endpoints	

CCICCICCI	
CCICCICCI

3. INVESTIGATIONAL PLAN

3.1. Overview of Study Design

Study TAS-120-203 is an open-label, nonrandomized, multicenter Phase 2 study evaluating the combination of futibatinib and pembrolizumab in patients with advanced or metastatic UC who are not candidates to receive a platinum-based treatment regimen.

The design is briefly summarized in Figure 1.

Abbreviations: FGFR=fibroblast growth factor receptor; I.V.=intravenous; mg=milligrams; PD=progressive disease; PO=oral; QD=daily; Q3W=every 3 weeks; Tx=treatment.

Figure 1: Study Schema

A treatment cycle is defined as 21 days. All enrolled patients will receive the same treatment regimen:

- Futibatinib at an oral (PO) dose of 20 mg daily (QD); and
- Pembrolizumab at an intravenous (I.V.) dose of 200 mg every 3 weeks (Q3W).

Treatment will continue until disease progression, unacceptable toxicity, or any other of the criteria for treatment discontinuation is met; of note, pembrolizumab may be administered for a maximum of 35 doses or a maximum duration of 2 years, whichever is earlier.

The study will begin with a safety lead-in period. During this period, a total of 6 patients with advanced or metastatic urothelial carcinoma will be enrolled and treated for at least one 21-day cycle. Patients will be enrolled into this initial safety lead-in period without regard for *FGFR* alteration status.

After the first 6 patients have completed one cycle of treatment, the first safety analysis will occur. After confirmation of the safety of the combination, a total of 20 additional patients will be enrolled into each of the following 2 cohorts:

- **Cohort A:** Patients with UC and *FGFR3* mutation or *FGFR* fusion/rearrangement. Patients will be enrolled based on local results but tissue samples will be archived for retrospective confirmation at a central lab using next generation sequencing (NGS).
- **Cohort B:** All other patients with UC (including patients with other *FGFR* or non-*FGFR* aberrations and patients with WT [non-mutated] tumors)

A second safety analysis will occur after enrollment of a total of 10 patients (including the 6 patients from the safety lead-in), in order to confirm the safety profile of the combination before proceeding to the enrollment of the remaining patients in Cohorts A and B.

Please note: at each safety analysis, the combination of futibatinib and pembrolizumab will be considered intolerable if the incidence of unacceptable toxicity including dose-limiting toxicity (as defined in [Section 5.2](#)) is $\geq 33\%$. If the combination is determined to be intolerable, the study may continue with a reduced dose of futibatinib (16 mg QD) if medically appropriate in the opinion of the Investigator and Sponsor.

Of note, the 6 patients initially enrolled in the safety lead-in period will also be assigned to the respective cohort based on *FGFR* alteration, such that each cohort will contain a minimum of 20 and a maximum of 26 patients.

3.2. Study Periods and Visits for Each Patient

The study periods / visits described in this section are defined for all patients. Please see [Table 1](#) (Schedule of Events) for an outline of all assessments to be performed during each study period / visit.

For all patients, the Safety Assessment Period begins at the time the informed consent form (ICF) is signed and continues until at least 90 days after the last dose of study therapy. After the 30-day Safety Follow-Up Visit (see below), patients who have not started treatment with a new anti-cancer therapy will be assessed for study therapy-related serious adverse events (SAEs) only.

For each patient, the Study Duration is defined as the time from day of ICF signature to the last day of Disease Assessment Follow-up / Survival Follow-up (see below).

3.2.1. Screening Period

The Screening Period is defined as the time from when the patient signs the ICF until the date of first dose of study therapy. Determination of eligibility is based on the entry criteria enumerated in [Section 4](#). No protocol-specific procedures or assessments may be performed prior to completion of the ICF, except for procedures that represent standard-of-care.

3.2.2. Treatment Period and End of Treatment Visit

Treatment discontinuation may occur for any of the reasons listed in [Section 4.4](#). The treatment period is the time from first dose of study therapy (Day 1) to the date of last dose of study therapy. An end-of-treatment (EOT) visit must be performed within 7 days after the decision is made to discontinue all study therapy; at this visit, every effort should be made to perform the assessments outlined in [Table 1](#). For patients who discontinue at a planned study visit, that visit may be considered the EOT visit if all assessments required at EOT are performed.

3.2.2.1. Safety Follow-Up Period and 30-Day Safety Follow-Up Visit

The safety follow-up period is the time from the date of last dose of study therapy through the safety follow-up visits, which must be performed 30, 60 and 90 days (± 3 days) following the last dose of study therapy. If the patient starts new anticancer therapy within 30 days of the last dose of study therapy, the 30-day safety follow-up visit should be performed before the start of new anticancer therapy. Every effort should be made to perform the assessments outlined in [Table 1](#). If the patient is unable to return to the study site, a follow-up phone call can be made by the study site to collect any new safety information that occurred during the safety follow-up period.

3.2.3. Post-Discontinuation Considerations

Patients who discontinue without documented disease progression should continue to undergo tumor assessments according to the Schedule of Events (that is, every 9 weeks ± 7 days) until progressive disease (PD) is documented, new anticancer therapy is initiated, the study is terminated, or the patient dies, withdraws consent, or is lost to follow-up).

3.2.4. Survival Follow-up

Once disease progression is confirmed or new anticancer therapy is initiated, whichever occurs first, the survival follow-up period begins. During this period, the patient or family should be contacted for survival follow-up every 12 weeks (± 2 weeks) until patient withdraws consent or the study is terminated early by the Sponsor. In addition, all subsequent anticancer treatments will be recorded.

3.2.5. Study Completion and Study Extension

The study will be considered complete when:

- Survival events (deaths) have been reported for 75% of enrolled patients; or
- The trial is halted early for any reason.

Following Study Completion, patients deriving benefit from study therapy in the opinion of the Investigator and Sponsor may be permitted to continue treatment with futibatinib in a Study Extension phase. During Study Extension, patients may receive treatment until withdrawal criteria are met.

During this period, all safety assessments are to continue according to the schedule in [Table 2](#). However, electronic data collection will be reduced. Specifically, study extension data collection is to include, at a minimum:

- Study drug administration;
- Study drug accountability;
- SAEs;
- Non-serious AEs that are related to study treatment or result in treatment discontinuation; and
- Any cases of pregnancy, overdose, or medication error.

4. SELECTION AND WITHDRAWAL OF PATIENTS

4.1. Inclusion Criteria

A patient must meet all of the following criteria to be eligible for participation in this study; waivers will not be granted for any of the eligibility criteria.

1. Histologically confirmed advanced or metastatic UC in patients who have not received systemic treatment for advanced metastatic disease. For patients who received prior adjuvant/neoadjuvant chemotherapy or chemo-radiation for urothelial carcinoma, a treatment-free interval >12 months between the last treatment administration and the date of recurrence is required in order to be considered treatment-naïve in the metastatic setting.
 - a. In safety lead-in: enrollment regardless of FGFR status
 - b. Cohort A: must have an *FGFR3* mutation or *FGFR1-4* fusion/rearrangement
 - c. Cohort B: all other patients with UC (including patients with other FGFR or non-*FGFR* genetic aberrations and patients with WT [nonmutated] tumors)
2. Unfit for or intolerant to standard platinum-based chemotherapy as defined by any one of the following criteria:
 - a. Chronic kidney disease characterized by the estimated creatinine clearance rate (eCCr) per Cockcroft-Gault formula of <60 mL/min or estimated glomerular filtration rate (eGFR) of <60 mL/min/1.73 m², corresponding to NCI-CTCAE v.5.0 Grade ≥ 2
 - b. Impaired hearing (measured by audiology) of >25 dB at two contiguous test frequencies in at least one ear, corresponding to NCI-CTCAE v.5.0 Grade ≥ 2
 - c. Peripheral sensory neuropathy Grade ≥ 2 by NCI-CTCAE v.5.0
 - d. Patient refusal
 - e. In the opinion of the Investigator, the patient is considered ineligible to receive any platinum-based chemotherapy
3. Be willing and able to provide written informed consent for the trial.
4. Be ≥ 18 years of age.
5. Have an Eastern Cooperative Oncology Group (ECOG) performance status (PS) of 0 to 1.
6. Adequate organ function as defined by the following criteria:
 - a. Absolute neutrophil count (ANC) $\geq 1.5 \times 10^9/L$
 - b. Platelet count $\geq 100,000/mm^3$
 - c. Hemoglobin $\geq 9.0 \text{ g/dL}$
 - d. Alanine aminotransferase (ALT) and aspartate aminotransferase (AST) $\leq 2.5 \times$ upper limit of normal (ULN); if liver function abnormalities are due to underlying liver metastasis, AST and ALT $\leq 5.0 \times$ ULN.

- e. Total bilirubin $\leq 1.5 \times$ ULN, or $\leq 3.0 \times$ ULN for patients with Gilbert's syndrome.
- f. Creatinine clearance (Ccr) (calculated or measured value): ≥ 30 mL/min. For calculated Ccr, use the Cockcroft-Gault formula.
- g. International normalized ratio (INR) OR prothrombin time $\leq 1.5 \times$ ULN unless participant is receiving anticoagulant therapy as long as prothrombin time or aPTT is within therapeutic range of intended use of anticoagulants
- h. Phosphorus < 1.5 ULN

7. Adequate recovery from the side effects of any prior therapy for nonmetastatic disease (generally defined as recovery of all AEs due to \leq Grade 1 or baseline; however, patients with \leq Grade 2 neuropathy, anemia, alopecia, and skin pigmentation may be eligible).
8. Have provided archival tumor tissue sample or newly obtained core or excisional biopsy of a tumor lesion not previously irradiated. Formalin-fixed, paraffin embedded tissue blocks are preferred to slides. Newly obtained biopsies are preferred to archived tissue.
9. Have a measurable disease per RECIST 1.1, as assessed by the local site Investigator/radiology. Lesions situated in a previously irradiated area are considered measurable if progression has been demonstrated in such lesions.
10. A male patient must agree to use contraception during the treatment period and for at least 6 months following the last dose of study treatment.
11. A female patient is eligible to participate if she is not pregnant, not breastfeeding, and at least one of the following conditions applies:
 - a. Not a woman of childbearing potential (WOCBP).
 - b. A WOCBP who agrees to follow contraceptive guidance during the treatment period and for at least 6 months after the last dose of study treatment.
 - c. A WOCBP who has a negative serum pregnancy test within 7 days prior to treatment.
12. Ability to take medications orally (feeding tube is not permitted).
13. Willing and able to comply with scheduled visits and study procedures.

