Thyroid Function Tests	X	X			X				Every 6 weeks until discontinuation of pembrolizumab.	
Pregnancy test	X						X		Serum pregnancy test required within 7 days prior to first dose for WOCBP. Additional testing (urine or serum) as required per local practice.	
Ophthalmological examination	X			See Note					Examination to be performed by an ophthalmologist or qualified delegate. At screening, 4-6 weeks after first dose, and as indicated if symptoms or signs of mineral deposits. In cases of retinal pigment epithelial detachment, events should be monitored at 2-3-week intervals.	
CCI				X					CCI	

Futibatinib (TAS-120)
Protocol TAS-120-203 – Amendment 1

Evaluation	Screening (Within 28 days of 1 st dose)	Treatment Period (1 cycle =21 days)					Safety Follow-up		Survival Follow-up Period (every 12±2 weeks)	Notes		
		Cycle 1			Cycle ≥2							
		D1 (-1 day)	D8 (-1 day)	D15 (-1 day)	D1 (-1 day)	End of Cycle (±7days)	End of Treatment (+0-7 days)	30, 60, and 90 days after last dose (±3 days)				
Blood sample for CCI assessment		X			X		X			CCI		
Tumor tissue collection for CCI assessment	X				X					Mandatory tissue collection at baseline (archival or new tumor biopsy). Optional tumor biopsy to be performed at Day 1 of Cycle 2 only.		
Tumor assessments (CT/MRI)	X					(X)	X	X	X	At baseline and the end of every 3 cycles (±7 days), or as clinically indicated, until radiologic PD or initiation of new anticancer therapy (whichever comes first). For patients who discontinue treatment for reasons other than radiographic disease progression, imaging will be performed at EOT, (if the prior scan was performed ≥9 weeks before EOT) and during Survival Follow-up until radiologic disease progression or initiation of new anticancer therapy (whichever occurs first).		
Survival status									X	For all patients, unless patient withdraws consent or the study is terminated early by the Sponsor.		

Table 2: Schedule of Events – Study Extension Phase

	Treatment Period (1 cycle = 21 days)		Safety Follow-Up 30, 60, and 90 (± 3 days) After Last Dose	Notes
	Daily	At Least Every 3 Cycles		
Physical examination		X	X	Within 24 hours prior to dosing on D1 of the cycle.
Vital signs		X	X	Heart rate, blood pressure, body temperature, and respiration rate.
Weight		X	X	
Ophthalmological examination		(X)	X	As needed due to local requirements, physician judgment, and/or symptoms or signs of mineral deposits.
ECOG performance status		X	X	Within 24 hours prior to dosing on D1

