- d. Chronic diarrhea diseases considered to be clinically significant in the opinion of the Investigator
- e. Congenital long QT syndrome, or any known history of torsade de pointes, or family history of unexplained sudden death
- f. Have an active autoimmune disease that has required systemic treatment in the past 2 years (that is, with use of disease modifying agents, corticosteroids, or immunosuppressive drugs). Replacement therapy (for example, thyroxine, insulin, or physiologic corticosteroid replacement therapy for adrenal or pituitary insufficiency) is not considered a form of systemic treatment and is allowed.
- g. Have a history of (noninfectious) pneumonitis that required steroids or has current pneumonitis.
- h. Have had an allogenic tissue/ organ transplant.

10. Has known human immunodeficiency virus (HIV) and/or history of Hepatitis B or C infections, or known to be positive for Hepatitis B antigen (HBsAg)/ Hepatitis B virus (HBV) DNA or Hepatitis C Antibody or RNA. Active Hepatitis C is defined by a known positive Hep C Ab result and known quantitative HCV RNA results greater than the lower limits of detection of the assay.
11. Has a history or current evidence of any condition, therapy, or laboratory abnormality that might confound the results of the study, interfere with the participant's participation for the full duration of the study, or is not in the best interest of the participant to participate, in the opinion of the treating Investigator.
12. Have known active central nervous system metastases and/or carcinomatous meningitis. Patients with previously treated brain metastases may participate provided they are radiologically stable, that is, without evidence of progression for at least 4 weeks by repeat imaging (note that the repeat imaging should be performed during study screening), clinically stable, and without steroid treatment requirement for at least 1 month prior to the first dose of study treatment.
13. The patient is pregnant or breastfeeding.
14. Has a diagnosis of immunodeficiency or is receiving chronic systemic steroid therapy (in dosing exceeding 10 mg daily of prednisone equivalent) or any other form of immunosuppressive therapy within 7 days prior the first dose of study drug.

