5.6. Effective Contraception During Study

Female patients considered not to be of childbearing potential must have a history of being postmenopausal (no menses for 12 months without an alternative medical cause), or hysterectomy that is clearly documented in the patient's source documents.

For WOCBP, including female study participants and partners of male participants, effective contraception is required during the study and for 6 months after the last dose of study medication, or longer if necessary based on local requirements. Effective contraception is defined as follows:

- Combined (estrogen and progestogen containing) hormonal contraception associated with inhibition of ovulation:
 - Oral
 - Intravaginal
 - Transdermal
- Progestogen-only hormonal contraception associated with inhibition of ovulation:
 - Oral
 - Injectable
 - Implantable
- Intrauterine device
- Intrauterine hormone-releasing system
- Bilateral tubal occlusion
- Vasectomized partner with documentation of the success of the vasectomy
- Complete abstinence from heterosexual intercourse (periodic abstinence is not a safe method)

Male patients with partners who are WOCBP should use a male condom in combination with at least one of the effective contraception methods during the study and for 6 months or longer based on local requirements after the last dose of study medication. Donation of sperm or ova is not allowed during the study and for 6 months or longer based on local requirements following the last dose of study drug.

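### Inclusion criterion 11 offers contraception agreement and a negative pregnancy test as alternatives, so a woman of childbearing potential can meet it without agreeing to contraception, out of line with Protocol Section 5.6.

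*Protocol*

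**What the plan says.** Protocol Section 4.1 opens with "A patient must meet all of the following criteria to be eligible for participation in this study", and it allows no waivers. Criterion 11 then takes a woman who is not pregnant and not breastfeeding, and adds that "at least one of the following conditions applies". The three conditions, where WOCBP stands for a woman of childbearing potential, are:

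- (a) she falls outside the WOCBP group;
- (b) "A WOCBP who agrees to follow contraceptive guidance during the treatment period", an undertaking that also runs for 6 months or more beyond her final dose;
- (c) "A WOCBP who has a negative serum pregnancy test within 7 days prior to treatment".

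The synopsis uses the same connector. For men, criterion 10 offers no alternative: "A male patient must agree to use contraception during the treatment period", again with at least 6 months afterwards.

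Two other parts of the protocol deal with the same matters. Section 5.6 says that for WOCBP, female participants included, "effective contraception is required during the study and for 6 months after the last dose of study medication". The pregnancy-test note in Table 1 reads "Serum pregnancy test required" and applies to every WOCBP in the 7 days before first dose. Section 6 confirms a serum test at screening and at end of treatment.

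**The concern.** Read literally, condition (c) alone is enough for a WOCBP, so the agreement in (b) is optional at the point where entry is decided. Section 5.6 shows that the sponsor wants contraception from every WOCBP, and criterion 10 shows that the sponsor regards the agreement as something to secure before entry. For women the entry criterion does not secure it.

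What is at stake is patient safety. A negative test describes a woman's status at entry and gives no undertaking about the treatment period. Section 1.3.1 describes the pathway that futibatinib blocks as essential to the development of the embryo. The rule in Section 9.5.1 that treatment stops on pregnancy takes effect only after a pregnancy has occurred. No endpoint, sample size or analysis depends on this.

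**Working it through.** The protocol gives no figure to reproduce here. The check is one of logic, followed by a comparison with the rest of the protocol.

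**1. Criterion 11 as written.** It is met when: not pregnant AND not breastfeeding AND (a OR b OR c).

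**2. Apply it to a WOCBP who is not pregnant and not breastfeeding.** Condition (a) is false, so the criterion reduces to (b OR c).

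| Agrees to contraception (b) | Negative serum test (c) | Criterion 11 as written | Both duties in Section 5.6 and Table 1 covered at entry? |
|---|---|---|---|
| yes | yes | met | yes |
| no | yes | met | no: no agreement to contraception |
| yes | not done | met | no: no test |
| no | not done | not met | no |

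The second and third rows are the mismatches. The third has little consequence, because Table 1 and Section 6 demand the test separately before first dose. The second is the point at issue.

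**3. Does condition (b) exclude anyone in practice?** Every WOCBP must have the serum test, and pregnancy is barred by the stem of criterion 11 and by exclusion 13. A WOCBP who is otherwise eligible and tested on schedule will therefore normally satisfy (c) already. As joined, (b) then screens out practically no one, which is hard to read as intended.

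**4. Does another entry criterion secure the agreement?**

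- Inclusion 13 asks for willingness to comply with visits and study procedures. It does not name contraception, and whether contraception counts as a study procedure is arguable.
- Exclusion 11 lets the investigator keep out a patient where it "is not in the best interest of the participant to participate, in the opinion of the treating Investigator". It does not name contraception either.
- No other criterion mentions contraception for women.

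**5. Logic that matches the rest of the protocol.** Not pregnant AND not breastfeeding AND (a OR (b AND c)). For a WOCBP only the first row of the table then passes.

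**The case against.** The strongest reply is that the protocol already covers this. Section 5.6 imposes contraception on every WOCBP, and Section 12.1 binds the investigator to the whole protocol, so treating a woman who declines contraception would breach Section 5.6 whatever criterion 11 says. An investigator could also use inclusion 13 or exclusion 11 to turn her away. This stands, and it is why the point is minor. It does not make the criterion right. Eligibility is decided against Section 4.1, and a site would correctly record criterion 11 as met. The SAP's category of unmet entry criteria (Section 5.2.2, important deviations) would not flag her either.

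Four stronger readings might be inferred, and the documents do not support them.

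- **That a negative test exempts a woman from contraception on study.** Meeting (c) waives nothing in Section 5.6.
- **That criterion 11 and Section 5.6 contradict each other.** A site can follow both. They are misaligned, not incompatible.
- **That the long interval between scheduled pregnancy tests is part of this defect.** The tests fall at screening and end of treatment, with others left to local practice. That interval is the same for women who do agree to contraception, and rewording criterion 11 would not change it.
- **That the number of women exposed can be bounded.** Section 1.1 gives population incidence of bladder cancer by sex. Applying it to this trial would give at best an expected count of all women under an assumed sex ratio. It would say nothing about childbearing potential or refusal of contraception, and it would not be a ceiling.

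The consent form may also obtain the undertaking. Consent pages are not in the review copy, so this cannot be judged either way.

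**Conclusion.** The point holds as a drafting error in a stated eligibility rule: criterion 11 is wrong as written, in Section 4.1 and in the synopsis. The conclusion rests only on the plain meaning of the connector and on Section 5.6 applying to every WOCBP; it needs no numerical assumption.

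Severity is minor. The practical effect is limited by Section 5.6, the mandatory serum test, exclusions 11 and 13, inclusion 13 and the general duty to comply in Section 12.1. The women concerned are WOCBP with a negative test who do not agree to contraception. Their number is unknown and probably very small, and no figure should be attached to it. Power, type I error and every planned analysis are untouched.

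**What to change.** In Section 4.1 and in the synopsis, keep the opening of criterion 11 (not pregnant, not breastfeeding) and replace the three alternatives with two:

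- (a) not a WOCBP; or
- (b) a WOCBP who both agrees to contraceptive guidance, for the treatment period and at least 6 months beyond the last dose, and has a negative serum pregnancy test in the 7 days before treatment.

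The cost is a wording change in two places. Because it alters an eligibility criterion, it needs an amendment under Section 12.3: issued by the sponsor, signed by the investigator, with documented IRB/IEC approval. It can go into the next routine amendment. It adds no visit, test or duty for patients, since Section 5.6 and Table 1 already impose both requirements.
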